### 5.3. Lifestyle Considerations

Potential participants must be willing and able to adhere to the following lifestyle restrictions during the study to be eligible for participation:

1. Agree to follow all requirements outlined in Section 6.5, Concomitant Therapy, regarding prohibited and restricted therapy during the study.
2. Agree to follow all requirements that must be met during the study as noted in the Inclusion and Exclusion Criteria (eg, contraceptive requirements).

### 5.4. Screen Failures

Refer to Section 5.4 of the Master Protocol PLATFORMPAHPB2001 for handling of screen failures and use of participant identification, enrollment, and screening logs.

This study will use IWRS. The investigator will generate screening and enrollment logs directly from IWRS.

## 6. STUDY INTERVENTION AND CONCOMITANT THERAPY

### 6.1. Study Intervention(s) Administered

#### Description of Study Intervention

The JNJ-3989 supplied for this study will be provided as an aqueous clear, colorless to light yellow solution with 200 mg/mL of JNJ-3989 for SC injection, containing 0.5 mM sodium phosphate monobasic and 0.5 mM sodium phosphate dibasic in water as inactive ingredients (formulation G001). JNJ-3989 will be manufactured and provided under the responsibility of the sponsor. Refer to the IB for a list of excipients ([IB JNJ-3989](#)).

The nivolumab formulated as concentrate for solution for infusion will be supplied for this study by the sponsor as a 40 mg/4 mL solution for IV infusion. Refer to the prescribing information for a list of excipients.

**Table 2: Description and Administration of Study Intervention**

| Intervention Name  | JNJ-3989   | Nivolumab  |
|---|---|---|
| Type   | Drug  | Drug  |
| Dose Formulation   | Solution for injection (G001)   | Concentrate for solution for infusion   |
| Unit Dose Strength(s)  | 200 mg/mL   | 40 mg/4 mL  |
| Dosage Level(s)  | 200 mg Q1W for the first 4 weeks, then once every Q4W until Week 24                     | 0.3 mg/kg (1 intravenous [IV] infusion for Arm 1 or 3 IV infusions Q4W for Arm 2)**             |
| Route of Administration  | Subcutaneous injection* (preferably in the abdomen; upper arm or thigh is also allowed) | IV infusion over 30 minutes   |
| Use  | Investigational intervention  | Investigational intervention  |
| Investigational Medicinal Product (IMP)  | Yes   | Yes   |
| Non-investigational Medicinal Product/ Auxiliary Medicinal Product (NIMP/AxMP) | No  | No  |
| Sourcing   | Provided centrally by the sponsor   | Provided centrally by the sponsor   |
| Packaging and Labeling   | Each unit will be labeled with unique medication ID number                              | Commercial supplies will be sourced. Each unit will be labeled with unique medication ID number |
| Food/Fasting Instructions  | Regardless of food intake   | Not Applicable  |

\*Note: Administration into scar tissue or areas that are reddened, inflamed or swollen should be avoided. If injecting into the abdomen, avoid a 5 cm diameter circle around the navel.

\*\*Note: a tolerance of +/- 5% around the theoretical dose of 0.3 mg/kg will be applied to consider the necessary rounding and standard practice for the preparation and intravenous administration of drugs dosed by weight.

### **Packaging and Labeling of Study Intervention**

All study interventions will be packaged with each unit labeled with a unique medication ID number. Packaging and labeling of JNJ-3989 and nivolumab will be done in an open-label way. Commercial supplies of nivolumab will be sourced, and a clinical study label will be applied. Study intervention labels will contain information to meet the applicable regulatory requirements.

No study interventions can be repacked or relabeled without prior approval from the sponsor.

### **Study Intervention Administration**

Study intervention administration must be captured in the source documents and the case report form (CRF).

JNJ-3989 injections will be administered SC (preferably in the abdomen) at the study site and the approximate location should be recorded.

Prior to starting nivolumab treatment, the participant's most recent ALT value (tested by local or central lab) should be  $<3\times$  ULN with no change in autoimmune status. In case the administration of nivolumab would not be in the interest of the participant, this should be discussed with the sponsor.

Nivolumab injections will be administered as an IV infusion at the study site. The duration of the IV infusion will be approximately 30 minutes.

When both JNJ-3989 and nivolumab are administered at the same visit, JNJ-3989 should be administered first (preferably in abdomen) followed within approximately 30 minutes by IV infusion of nivolumab.

For a definition of study intervention overdose, refer to Section 6.8, Treatment of Overdose.

## **6.2. Preparation/Handling/Storage/Accountability**

### **Preparation/Handling/Storage**

All study intervention must be stored as specified on the product-specific labeling.

Refer to the pharmacy manual/study site investigational product and procedures manual for additional guidance on study intervention preparation, handling, and storage.

### **Accountability**

The investigator is responsible for ensuring that all study intervention received at the site is inventoried and accounted for throughout the study. The dispensing of study intervention to the participant, and the return of study intervention from the participant (if applicable), must be documented on the intervention accountability form. Participants must be instructed to return all original containers, whether empty or containing study intervention. The study intervention administered to the participant must be documented on the intervention accountability form. All study intervention will be stored and disposed of according to the sponsor's instructions. Study site personnel must not combine contents of the study intervention containers.

Study intervention must be handled in strict accordance with the protocol and as indicated on the container label, and must be stored at the study site in a limited-access area or in a locked cabinet under appropriate environmental conditions. Unused study intervention must be available for verification by the sponsor's study site monitor during on-site monitoring visits. The return to the sponsor of unused study intervention, or used returned study intervention for destruction, will be documented on the intervention return form. When the study site is an authorized destruction unit and study intervention supplies are destroyed on site, this must also be documented on the intervention return form.

Potentially hazardous materials containing hazardous liquids, such as used ampules, needles, syringes and vials, must be disposed of immediately in a safe manner and therefore will not be retained for intervention accountability purposes.

Study intervention must be dispensed under the supervision of the investigator or a qualified member of the study site personnel, or by a hospital/clinic pharmacist. Study intervention will be supplied only to participants participating in the study. Study intervention may not be relabeled or reassigned for use by other participants. The investigator agrees neither to dispense the study intervention from, nor store it at, any site other than the study sites agreed upon with the sponsor. Further guidance and information for the final disposition of unused study intervention is provided in the Study Reference Manual.

### **6.3. Measures to Minimize Bias: Randomization and Blinding**

#### **Intervention Allocation**

##### *Procedures for Randomization and Stratification*

Participants will be randomly assigned to 1 of 2 intervention groups based on a computer-generated randomization schedule prepared before the study by or under the supervision of the sponsor. The randomization will be balanced by using randomly permuted blocks and will be stratified by absolute HBsAg level (<100 IU/mL, 100 to <1,000 IU/mL, and ≥1,000 IU/mL) at screening, as assessed by quantitative HBsAg assay. Based on this randomization code, the study intervention will be packaged and labeled for each participant. Participant numbers will be preprinted on the study intervention labels and assigned as participants qualify for the study and are assigned to intervention.

For more information on the interactive web response system (IWRS), refer to Section 6.3 of the Master Protocol PLATFORMPAHPB2001.

#### **Blinding**

As this is an open-label study, blinding procedures are not applicable.

### **6.4. Study Intervention Compliance**

JNJ-3989 and nivolumab will be administered at the study site by qualified study site personnel as an SC injection and IV infusion, respectively, to assure compliance with study requirements. The details of each administration will be recorded in the source document and CRF (including date, start and stop times of the IV infusion or SC injection, volume prepared, and volume administered).

The dose of study intervention and study participant identification will be confirmed at the time of dosing by a member of the study site personnel other than the person administering the study intervention. The study intervention may not be used for any purpose other than that outlined in this protocol, including other human studies, animal investigations, or in vitro testing. Study site personnel will maintain a log of all study interventions administered. Study intervention supplies for each participant will be inventoried and accounted for.

Every effort should be made to have the study interventions administered as indicated in the [Schedule of Activities](#), especially during the first 4 weeks of dosing.

If a SC injection of JNJ-3989 was missed during the loading dose period (Week 1-4), the injection should be given as soon as possible but within 3 days after the scheduled time and with a minimum of 3 days between injections. Otherwise, the dose should be skipped and the next dose should be given at the next scheduled time point per the initial dosing schedule.

If after the loading dose period a SC injection of JNJ-3989 was missed or an IV infusion of nivolumab was missed, the injection or infusion should be given as soon as possible but within 2 weeks after the scheduled time. Otherwise, the dose should be skipped and the next dose should be given at the next scheduled time point per the initial dosing schedule.

In case of ALT elevation  $\geq 3x$  ULN during the first 4 weeks of dosing, administration of JNJ-3989 should be discussed with the sponsor.

If a participant's study intervention intake is not according to the protocol, the investigator will take the necessary measures to ensure future adherence to the protocol.

### 6.5. Concomitant Therapy

For general concomitant therapy considerations, refer to Section 6.5 of the Master Protocol PLATFORMPAHPB2001.

An overview of ISA-specific disallowed medication is provided in [Table 3](#).

For participants who consent to complete the optional FNA biopsy of the liver, any anticoagulants and antiplatelets are disallowed from baseline to at least 2 weeks after the completion of the last FNA biopsy. Use of low-dose aspirin is allowed except during the 7 days period preceding the FNA biopsies.

Note that locally approved COVID-19 vaccines (including those that received emergency use authorization or conditional marketing authorization) are allowed throughout the study, with the exception of the second dose of Sputnik V (which contains rAd5). Sputnik light which is the first dose of Sputnik V (with rAd26) is allowed.

During nivolumab treatment, the following recommendations should be applied to accommodate COVID-19 vaccination:

- COVID-19 vaccine and nivolumab should not be administered on the same day. If required, nivolumab administration can be delayed by 2-5 days.
- The next nivolumab administration should be performed at the scheduled time.
- If required, skipping a nivolumab administration may be considered after consultation with the sponsor.

All COVID-19 vaccination-related data (eg, COVID-19 vaccination, AEs, AE management) should be appropriately captured in the CRF and source documents. Refer to the COVID-19 vaccine and/or nivolumab prescribing information for more details.

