| Nivolumab sparse PK: 2-6 hours post-dose                        |                       |                                       |         |          |          |         |         |         | X        | X        | X                            |
| Nivolumab sparse PK: 6-24 hours post-dose (Arm 2 only)          |                       |                                       |         |          |          |         |         |         | (X)      | (X)      | (X)                          |
| Exploratory Host Biomarkers                              |                       |                                       |         |          |          |         |         |         |          |          |                              |
| Whole blood RNA gene expression                                 |                       | X                                     |         |          |          |         | X       |         | X        |          | X                            |
| Whole blood single-cell profiling                               |                       | X                                     |         |          |          |         | X       |         | X        |          | X                            |
| Host serum proteins   |                       | X                                     |         |          |          |         | X       |         | X        |          | X                            |
| Optional FNA collection kk                           |                       | X ll                       |         |          |          |         |         |         |          |          | X                            |
| Antidrug antibodies to JNJ-3989                                 |                       | X                                     |         |          |          |         |         | X       |          |          | X                            |
| Antidrug antibodies to nivolumab                                |                       |                                       |         |          |          |         |         | X       | X        | X        | X                            |
| Blood sample collection for RO assay (nivolumab): mm |                       |                                       |         |          |          |         |         |         |          |          |                              |

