| Concomitant therapy oo                               | X                     | X                                     | X       | X        | X        | X       | X       | X       | X        | X        | X                            |
| Adverse events oo                                    | X                     | X                                     | X       | X        | X        | X       | X       | X       | X        | X        | X                            |

(X): optional or conditional sample; AFP: alpha-fetoprotein; ALT: alanine aminotransferase; AST: aspartate aminotransferase; CKD-EPI: Chronic Kidney Disease Epidemiology Collaboration; CRF: case report form; CRP: C-reactive protein; CT: computed tomography; D/d: day; DAIDS: Division of Acquired Immunodeficiency Syndrome; DBP: diastolic blood pressure; DNA: deoxyribonucleic acid; ECG: electrocardiogram; eGFR: estimated glomerular filtration rate; EOSI: end of study intervention; FNA: fine needle aspiration; FSH: follicle-stimulating hormone; FU: follow-up; GI: giga; HBe: hepatitis B core protein; HBe(Ag): hepatitis B e (antigen); HBc(Ag): hepatitis B core-related antigen; HBs(Ag): hepatitis B surface (antigen); HBV: hepatitis B virus; HCC: hepatocellular carcinoma; HIV-1 (-2): human immunodeficiency virus type 1 (type 2); HLA: human leukocyte antigen; ICF: informed consent form; IgM: immunoglobulin M; INR: International Normalized Ratio; ISA: intervention-specific appendix; MRI: magnetic resonance imaging; NA: nucleos(t)ide analog; PBMC: peripheral blood mononuclear cells; PK: pharmacokinetic; RNA: ribonucleic acid; RO: receptor occupancy; SBP: systolic blood pressure; T3: triiodothyronine; T4: thyroxine; TSH: thyroid-stimulating hormone; ULN: upper limit of normal; W: week; WD: withdrawal.

- a. All study intervention visits are to be scheduled relative to the baseline (Day 1) visit date. An unscheduled visit can be performed upon the investigator's discretion, in case of HBV DNA elevations, ALT elevations, other signs of worsening of liver disease, or for any other reason.
- b. At all visits, blood samples should be collected before administration/intake of study intervention (JNJ-3989, nivolumab) and NA, unless indicated otherwise.

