## 5.2. Exclusion Criteria

Any potential participant who meets any of the following criteria will be excluded from participating in the study:

|                           |   |
|---------------------------|---|
| A01
(adapted from M01) | 
Participants with evidence of hepatitis A virus infection (hepatitis A antibody IgM), HCV infection (HCV antibody), HDV infection (HDV antibody), hepatitis E virus (HEV) infection (hepatitis E antibody IgM), or HIV-1 or HIV-2 infection (laboratory confirmed) at screening.
 
Note:
 
 
– Participants with a positive HCV antibody test can be enrolled if they have negative HCV RNA at screening and documented negative HCV RNA at least 6 months prior to screening.
 
– Participants with a positive HDV antibody test may be enrolled after discussion with the sponsor if an active HDV co-infection can be ruled out by documentation of negative HDV RNA.
 
– Participants with a positive IgM antibody test for HEV infection may be enrolled after discussion with the sponsor if an active HEV infection can be ruled out by documentation of negative anti-HEV IgG.a
 
– Participants with a positive HIV-1 or HIV-2 antibody/antigen test at screening should have a confirmatory HIV RNA test, to rule out false positive results. They can be enrolled if they have a negative HIV RNA test at screening. Participants with evidence of HIV-1 or HIV-2 infection who are on antiretroviral treatment are excluded.
 
 |
|---------------------------|---|

a Negative HEV RNA may also be acceptable to rule out active HEV infection depending on local standard practices.

- A02 (adapted from M02) Participants with evidence of hepatic decompensation at any time point prior to or at the time of screening:
- Total bilirubin >1.5x ULNa, OR
  - Direct bilirubin >1.2x ULNb, OR
  - Prothrombin time >1.3x ULN (unless caused by anticoagulation therapy or vitamin K deficiency)b, OR
  - Serum albumin <3.2 g/dLb.
- M03 History or evidence of clinical signs or symptoms of hepatic decompensation, including but not limited to: portal hypertension, ascites, hepatic encephalopathy, esophageal varices.

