### **8.7. Exploratory Host Biomarkers**

The study includes collection of blood samples for exploratory analysis of host blood biomarkers at the host RNA, protein, and cell level. Sampling will be performed at the time points indicated in the [Schedule of Activities](#). Leftovers of other samples might also be used for exploratory research of host and viral markers.

Samples can only be used for research related to study intervention or HBV infection or may be used to develop tests/assays related to study intervention or HBV infection.

A FNA biopsy sample may be collected from participants who consent separately to this component of the study (as permitted by local regulations). If participants agree to undergo an optional FNA biopsy of the liver, following local standard practice, the biopsy location will be identified and/or guided with ultrasound and the FNA biopsy samples will be collected after application of local anesthesia to allow for exploratory biomarker research.

The FNA biopsy procedure should be preceded and followed by standard medical monitoring according to local medical practice. This may include an overnight stay at the investigator's discretion. Prior to each FNA biopsy, a recent ( $\leq 2$  weeks) coagulation and hematology panel are required to ensure normal platelet count and normal coagulation parameters. The use of local laboratories may be allowed at the investigator's discretion. Optional FNA biopsy will only be completed at selected sites that have expertise and capacity to perform FNA biopsy. Intrahepatic immune response to treatment will be assessed in FNA biopsy samples.

Infiltrating immune cells will be used for the evaluation of immune responses, which can be compared to responses in PBMCs.

These analyses will be performed at the sponsor's discretion, will always be under the sponsor's supervision, and may be reported separately.

More information is provided in Section 8.8 of the Master Protocol PLATFORMPAHPB2001.

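### For participants who consent to the optional liver FNA, this ISA's anticoagulant and antiplatelet ban starts on the day of the first puncture, so it guarantees no hold beforehand (minor; mainly non-aspirin antiplatelets)

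*Protocol*

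**What the plan says.** Protocol Section 6.5 sets two rules for participants who consent to the optional FNA. The general rule is that "any anticoagulants and antiplatelets are disallowed from baseline to at least 2 weeks after the completion of the last FNA biopsy". The exception follows directly: "Use of low-dose aspirin is allowed except during the 7 days period preceding the FNA biopsies". The section opens by deferring to another document: "For general concomitant therapy considerations, refer to Section 6.5 of the Master Protocol PLATFORMPAHPB2001".

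Baseline means Day 1 in this ISA. Footnote a of the Schedule of Activities (Section 1.3.1) states: "All study intervention visits are to be scheduled relative to the baseline (Day 1) visit date". The row "Optional FNA collection" is marked at W0/D1 and at Week 24, and Section 1.3.2 adds a conditional collection at FU Week 48. Footnote ll treats a later visit as a fallback when the Day 1 FNA cannot be done, and says this is not a deviation.

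Before each FNA, Section 8.7 asks for recent laboratory results, no more than 2 weeks old: a "coagulation and hematology panel are required to ensure normal platelet count and normal coagulation parameters". It also limits where the procedure is done: "Optional FNA biopsy will only be completed at selected sites that have expertise and capacity to perform FNA biopsy".

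**The concern.** A ban on drugs that impair clotting or platelet function protects against bleeding at a puncture only if it starts early enough for the effect to wear off. Here the ban and the first puncture start on the same day. The aspirin sentence shows that the authors thought an interval before the puncture mattered, and for a Day 1 FNA that interval already reaches back into screening. The general ban has no such reach. It is also the only medication restriction in Section 6.5 that opens at baseline: every window in Table 3 opens at screening or earlier.

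What is at stake is a bleeding precaution for an optional research puncture of the liver. For the first FNA, the decision that a non-aspirin antiplatelet has been stopped long enough rests on site judgement, not on a rule in this ISA.

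**Working it through.** The plan states no figure to reproduce. The check compares dates and then asks whether any other ISA text fills the interval.

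**Inputs**
- Ban start: baseline (Protocol Section 6.5), which is Day 1 (Section 1.3.1, footnote a).
- FNA time points: Day 1 and Week 24 = Day 169 (Section 1.3.1); FU Week 48 = follow-up Day 337, counted from the Week 24 visit (Section 1.3.2).
- Low-dose aspirin hold: 7 days (Section 6.5).
- Ban end: at least 14 days after the last FNA (Section 6.5).
- Screening: 42 days, with FNA consent scheduled in it (Sections 1.3.1 and 5).

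**Guaranteed drug-free days = FNA day − ban start day** (nominal visit days)

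| FNA | Calculation | Days |
|---|---|---|
| Day 1 | 1 − 1 | 0 |
| Week 24 | 169 − 1 | 168 |
| FU Week 48 | 169 + (337 − 1) = 505; 505 − 1 | 504 |

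Only 1 of the 3 time points lacks an interval. If the first FNA slips to a later visit, the interval equals the delay.

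**Length of the ban for a consenter**
- Last FNA at Week 24: 169 + 14 = 183; 183 − 1 = 182 days; 182 / 7 = 26 weeks.
- Last FNA at FU Week 48: 505 + 14 = 519; 519 − 1 = 518 days; 518 / 7 = 74 weeks.

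A regular user of these drugs could not comply, so the exposed group is limited to people who stop shortly before Day 1.

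**Does other ISA text supply the missing hold?**
- Exclusion M16 covers disallowed therapies taken before screening, but relies on Section 6.5 to define them. Section 6.5 disallows these drugs only from baseline, so M16 adds nothing.
- The pre-FNA panel can reveal an anticoagulant that alters the tests, if the sample was drawn on drug. A platelet count does not measure platelet function, so a non-aspirin antiplatelet effect goes undetected.
- Concomitant therapy is recorded at screening and Day 1. That shows use but sets no hold and no deferral rule.

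**Feasibility of a hold:** 42 days of screening exceeds 7 days, so an antiplatelet hold fits between FNA consent and Day 1 if consent is given at least a week before.

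**The case against.** The strongest objection is that the practical benefit in this trial is nil. The sample is final at 37 (18 and 19 per arm), and randomization is scheduled on Day 1, so every participant has reached Day 1. Any first FNA still outstanding already falls under the ban. This stands: the gain is to the written rule and to any ISA that reuses it.

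Second, Section 6.5 of the Master Protocol and the FNA consent form were not supplied, and either may set a hold. This stands too, and limits the point to what this ISA says.

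Third, the two rules differ in kind: aspirin is the one permitted drug and so needs a hold before each puncture, while the others are banned continuously. That explains the wording for later FNAs but not for the first, where the continuous ban has had no time to run. The objection does bear on the remedy: 7 days is the aspirin figure, and the documents give no interval for other drugs. A uniform 7-day minimum for every anticoagulant would rest on analogy alone.

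Fourth, exposure is very small. Participants are under 56, M10 excludes significant cardiac disease, M11 can exclude significant vascular illness, and the sites are selected and follow local practice. Section 2.3.2.2 lists pain and discomfort and cites a series of over 1000 liver-allograft FNAs without complications. All of this supports a low grading.

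A reader might infer from exclusion A02, which excuses a prolonged prothrombin time "unless caused by anticoagulation therapy or vitamin K deficiency", that anticoagulated participants would go to FNA. The documents do not support that. A02 concerns hepatic decompensation at study entry, and a participant with a prolonged prothrombin time would fail the separate FNA requirement for normal coagulation. Nor does A02 say anything about antiplatelets.

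**Conclusion.** The point holds as a minor gap in a stated safety rule. Within this ISA, the guaranteed hold before a Day 1 FNA is 0 days for anticoagulants and non-aspirin antiplatelets, against 7 for low-dose aspirin. Because the panel gives some protection against anticoagulants, the gap is mainly about non-aspirin antiplatelets.

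It rests on reading baseline as Day 1, which the ISA's own usage supports, and on the FNA being done as scheduled. It is conditional on the Master Protocol not already setting a hold. The number of consenters on such drugs is not given; it cannot exceed 37 and is probably very small or zero.

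Two further readings go too far. One is that participants were punctured while on these drugs: the documents describe a rule, not what happened. The other is that there is a 7-day deficit for all drugs: no required interval is stated for anything but aspirin. No endpoint, estimand or analysis is affected.

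**What to change.** In Section 6.5, replace the baseline start with wording such as: *from before the first FNA biopsy (at least 7 days for antiplatelets, matching the aspirin rule; a drug-appropriate interval, set by the medical team, for anticoagulants)*. In Section 1.3.1, add to footnote ll that the Day 1 FNA is deferred if the hold was not met; the footnote already allows deferral. If Section 6.5 of the Master Protocol already sets a hold, a cross-reference is enough.

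The cost is one phrase and one clause, plus the FNA consent form if it repeats the rule. The downside is an occasional lost pre-treatment sample, because JNJ-3989 starts on Day 1 and a deferred FNA would no longer be pre-treatment. With all participants past Day 1, the change is best made when the document is next opened or when the wording is carried into another ISA.
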